**Protocol Number:**

**Protocol Title:** A Phase II Study of PD-0332991 Treatment of Patients with Advanced Hepatocellular Carcinoma

**Study Objectives:**                      **Primary Objective:**

To assess the time to disease progression (TTP) in patients with advanced hepatocellular carcinoma treated with PD-0332991

**Secondary Objectives:**

To assess the safety and tolerability of PD-0332991 in patients with advanced hepatocellular carcinoma

To assess overall survival (OS) in patients with advanced hepatocellular carcinoma treated with PD-0332991

To assess the response rate (RR) in patients with advanced hepatocellular carcinoma treated with PD-0332991

Study Population:	Patients with inoperable, therapy-refractory advanced HCC
Study Design:	Single-institution study
Investigational Product:	PD-0332991
Dosage Form:	Capsule
Route of Administration:	Oral
Dosage and Treatment Schedule:	125 mg oral capsules daily for 21 days, followed by week rest, with cycle consisting of 28 days, in repeated cycles
Endpoints:	Time to disease progression (TTP) defined as time from entry on study to progression of disease.  Safety and Tolerability  Overall survival (OS)  Response rate (RR)
Duration of Treatment:	Until progression of disease
Duration of Subject Participation in Study:	Progression of disease, subject withdrawal or death
Duration of Follow-up:	Subjects will be followed after disease progression with visits at 28 days, and 56 days post treatment discontinuation and every 3 months until death, subject is lost to or declines follow up. Safety data will be collected until AEs are resolved after the last dose of treatment is given.

Number of Subjects Required:	19 evaluable
Maximum Total AcruaI:	25

## **1.0 Background**

### **1.1 Current Treatment of Hepatocellular Carcinoma**

Hepatocellular carcinoma (HCC) is the fifth most common cancer worldwide and the third most frequent cause of cancer-related mortality (El-Serag et al. 2007). While the majority of HCC cases occur in developing countries due to the high prevalence of hepatitis B (HBV) and hepatitis C (HCV) infection, the incidence of HCC has significantly increased in the United States over the last three decades and is predicted to remain a major health risk for future generations (El-Serag 2004). To date, surgical resection and liver transplantation are considered the main curative treatment options for HCC (El-Serag et al. 2006). However, the majority (~75%) of patients present with advanced tumor stage and poor liver function, rendering the patient ineligible for surgical interventions (Siegel et al. 2008). Furthermore, until very recently, there have been no standard systemic therapies for advanced HCC, as classical cytotoxic drugs (administered singularly or in combination) have not led to reproducible response rates or survival benefit (Llovet and Bruix 2003).

Recently, the advent of promising “targeted” therapies has introduced new possibilities for the treatment of otherwise chemo-resistant tumors. Specifically, the multikinase inhibitor sorafenib displayed a significant increase in progression-free and overall survival of patients with advanced or metastatic HCC in two randomized phase III trials (Llovet et al. 2008, Cheng et al. 2009). However, even with such favorable and landmark results, the response rate to sorafenib was remarkably low, and the overall benefits were reported to be relatively modest with a response rate of only 2% in both pivotal phase III trials. Thus, while the treatment of advanced HCC with targeted therapy has generated encouraging results, there is still a critical need for more key molecular targets and targeting compounds for truly successful therapeutic intervention.

### **1.2 Mechanism of Action, Pre-clinical and Clinical Data for PD-0332991**

PD-0332991 is an orally available, pyridopyrimidine-derived, selective inhibitor of cyclin dependent kinase 4/6 (CDK4/6) (Fry et al. 2004, Toogood et al. 2005). Functionally, PD-0332991 is a potent and highly selective inhibitor of CDK4/6-cyclin D1 kinase activity, which ultimately results in the inhibition of retinoblastoma (Rb) protein phosphorylation and cell cycle arrest. In vitro and in xenograft models, PD-0332991 was observed to inhibit a panel of Rb-positive, solid tumor cell lines (Fry et al. 2004). A phase I clinical trial with PD-0332991 in patients with Rb-positive advanced solid tumors demonstrated a mean therapeutic dose (MTD) of 125 mg/d for 3 out of 4 weeks and a principal, dose-limiting toxicity of myelosuppression (O’Dwyer et al. 2007). Furthermore, in the context of metastatic teratoma, PD-0332991 as a single agent provided durable progression-free survival in excess of 18 months (Vaughn et al. 2009). A phase II trial of PD-0332991 in the treatment of mantle cell lymphoma (MCL) is currently ongoing, as well as combination studies with letrozole for breast cancer and with bortezomib and dexamethasone for multiple myeloma.

In preclinical studies, PD-0332991 has extensive cytostatic activity. In hepatoma cell lines this effect is dependent on the RB protein, and PD-0332991 was observed to be significantly more effective than the only currently approved therapeutic agent, sorafenib. Furthermore, in animal models, PD-0332991 was effective at inhibiting the proliferation of

hepatocytes in liver, indicating that effective doses can be achieved in vivo (Rivadeneira et al. 2010). Finally, ongoing studies suggest that PD-0332991 is a potent inhibitor of tumor proliferation in the context of xenograft models. Combined, these findings suggest that PD-0332991 could be effective in the treatment of therapy refractory HCC.

### **1.3 Rationale for Treatment of Advanced HCC with PD-0332991**

The majority of patients with HCC present with advanced disease, and there are currently very limited options available that yield reproducible response rates or significant overall survival benefits. (Llovet, 2003) While targeted therapies such as sorafenib point the way to new, promising treatment options, there is an unmet need for trials using these agents in advanced HCC. Pre-clinical data with PD-0332991 demonstrates potent target-specificity and significant inhibition of tumor cell growth in vitro and in xenografts (Fry et al. 2004, Rivadeneira et al. 2010). Furthermore, early clinical studies demonstrate acceptable toxicities of PD-0332991, a critical factor in the treatment of patients with advanced HCC that is often associated with compromised liver function (Bruix and Sherman 2005). Thus, PD-0332991 represents an ideal candidate for the treatment of patients with advanced HCC.

## **2.0 Study Objectives and Endpoints**

### **2.1 Study Objectives:**

#### **2.11 Primary Objective**

To assess the time to disease progression (TTP) in patients with advanced hepatocellular carcinoma treated with PD-0332991.

#### **2.12 Secondary Objectives**

1. To assess the safety and tolerability of PD-0332991 in patients with advanced hepatocellular carcinoma.
2. To assess overall survival (OS) in patients with advanced hepatocellular carcinoma treated with PD-0332991.
3. To assess the response rate (RR) in patients with advanced hepatocellular carcinoma treated with PD-0332991.

### **2.2 Study Endpoints:**

1. Time to disease progression (TTP) defined as time from enrollment on study to documented progression of disease.
2. Safety and Tolerability including adverse events, and significant laboratory abnormalities

3. Overall survival (OS) defined as the time from entry on trial to the time of death, from any cause.
4. Objective Response Rate defined as the proportion of subjects with either a confirmed CR or a confirmed PR as determined using modified RECIST (Version 1.1) criteria

### **3.0 Study Design**

This is an open-label non-randomized single-institution study for subjects with inoperable, recurrent/refractory advanced hepatocellular carcinoma (HCC). Subjects must have failed or be intolerant of standard first line therapy, sorafenib (Nexavar®). Eligible subjects will receive 125 mg PD-0332991 capsules orally once daily, administered days 1-21 of a 28-day cycle, in repeated cycles.

Subjects will be permitted to receive protocol directed therapy until disease progression by modified RECIST (Version 1.1) (Response Evaluation Criteria in Solid Tumors) guidelines or clinical progression, unacceptable toxicity, withdrawal of consent or death. Tumor response assessment will be performed by the Investigator and will consist of evaluation by CT or MRI using modified RECIST (Version 1.1) guidelines every 8 weeks. Subjects who discontinue therapy for disease progression or other reasons will be followed for safety on Day 28 ( $\pm$  3 days), Day 56 ( $\pm$  3 days) and every 3 months thereafter or until death, from the last administration of protocol –directed therapy.

Subjects will be continuously assessed for evidence of acute and cumulative toxicity. Vital signs, Physical examinations, performance status, laboratory safety tests will be obtained and assessed prior to drug administration and at regular intervals throughout the study. Toxicity will be evaluated every 2 weeks during the first 3 cycles and thereafter monthly (once per cycle) by the Investigator according to National Cancer Institute (NCI) Common Terminology Criteria for Adverse Events (CTCAE), Version 4.0 (which can be viewed on-line at the following NCI web site: <http://ctep.cancer.gov/reporting/ctc.html>).

### **4.0 Patient Recruitment, Eligibility, and Exclusion**

Subjects will be recruited from the outpatient oncology and multidisciplinary liver clinics of Thomas Jefferson University.

#### **4.1 Eligibility Inclusion Criteria**

1. Male or female, age  $\geq$ 18 years with HCC refractory to currently available therapies.
2. Documented HCC by pathologic criteria.

Recommendations for diagnosis of HCC have been issued in a guideline from the American Association for the Study of Liver Diseases, which can be accessed through the AASLD web site at <http://www.aasld.org/practiceguidelines/Pages/default.aspx>.

3. Subject must be able to give written informed consent and be able to follow protocol requirements
4. Life expectancy greater than 3 months
5. Be Child's-Pugh class A or B
6. ECOG Performance status of  $\leq 2$
7. If female of childbearing potential must have negative pregnancy test at screening and may not be breast-feeding
8. Females of child-bearing potential (< one year post-menopausal with documented FSH greater than 30 IU/L or surgically not sterile), must agree to practice an effective method of avoiding pregnancy (including oral or implanted contraceptives, intrauterine device, condom, diaphragm with spermicidal, cervical cap, abstinence or sterile sex partner) from the time informed consent is signed through follow-up. Males must agree to take appropriate precautions to avoid fathering a child from screening through follow-up.
9. No other active malignancy requiring treatment in the last 3 years other than adequately treated non-melanomatous skin cancer, adequately treated cervical carcinoma in-situ, superficial adequately treated bladder cancer or prostatic intraepithelial neoplasia without evidence of prostate cancer.
10. Adequate bone marrow, liver and renal function as assessed by the following:
  - Hemoglobin  $\geq 8$  g/dL
  - WBC  $\geq 4,000$ /uL
  - Absolute neutrophil count  $\geq 1,500$ /uL
  - Platelets  $\geq 75,000$ /uL
  - Total bilirubin  $\leq 1.5$  times ULN
  - ALT and AST  $\leq 5$  times ULN
  - Creatinine  $\leq 1.5$  times ULN
  - Albumin  $\geq 2.5$  mg/dL
11. Subjects who have received previous radiotherapy, loco-regional, or systemic therapy are eligible. A minimum interval of 4 weeks since the last anti-cancer treatment of any kind is required.
12. Subjects with brain metastases or a history of previously treated brain metastasis are eligible but must:
  - Have been treated by surgery or stereotactic radiosurgery (SRS) at least 4 weeks prior to enrollment

- AND have a baseline MRI or CT that shows no evidence of active intracranial disease
- AND be off steroids for at least 1 week prior to study enrollment

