#### **Measurable Disease**

Measurable lesions are defined as those that can be accurately measured in at least one dimension (longest diameter to be recorded) as  $\geq 20$  mm with conventional techniques (CT, MRI, x-ray) or as  $\geq 10$  mm with spiral CT scan. All tumor measurements must be recorded in millimeters (or decimal fractions of centimeters).

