#### **Non-Measurable Disease**

All other lesions (or sites of disease), including small lesions (longest diameter  $< 20$  mm with conventional techniques or  $< 10$  mm using spiral CT scan), are considered non-measurable disease. Bone lesions, leptomeningeal disease, ascites, pleural/pericardial effusions, lymphangitis cutis/pulmonis, inflammatory breast disease, abdominal masses (not followed by CT or MRI), and cystic lesions are all non-measurable.

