#### **Target Lesions**

All measurable lesions up to a maximum of five lesions per organ and ten lesions in total, representative of all involved organs, should be identified as **target lesions** and recorded and measured at baseline. Target lesions should be selected on the basis of their size (lesions with the longest diameter) and their suitability for accurate repeated measurements (either by imaging techniques or clinically). A sum of the longest diameter (LD) for all target lesions will be calculated and reported at time of disease recurrence.

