#### **Non-Target Lesions**

All other lesions (or sites of disease) should be identified as **non-target lesions** and should also be recorded at time of disease recurrence. Non-target lesions include measurable lesions that exceed the maximum numbers per organ or total of all involved organs as well as non-measurable lesions. Measurements of these lesions are not required but the presence or absence of each should be noted throughout follow-up.

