## **6.2 Response Assessment**

Response is assessed on the basis of clinical, radiological, and pathological criteria. Standard imaging via MRI and/or CT scan will be used for evaluation of nodal disease based on RECIST criteria. These techniques should be performed with cuts of 10 mm or less in slice thickness contiguously. Spiral CT should be performed using a 5 mm contiguous reconstruction algorithm.

The subject's response will be assessed based on the response of the target lesions, the response of non-target lesions and the presence or absence of new lesions through out the course of the study.

Response Criteria for Target Lesions:

Complete Response (CR)	Disappearance of all target lesions
Partial Response (PR)	At least 30% decrease in the sum of the LD of target lesions, taking as reference the baseline sum LD
Progressive Disease (PD)	At least 20% increase in the sum of the LD of target lesions, taking as reference the smallest sum LD recorded since the treatment started or the appearance of one or more new lesions.
Stable Disease (SD)	Neither sufficient shrinkage to qualify for PR nor sufficient increase to qualify for PD, taking as reference the smallest sum LD recorded since the treatment started

Response Criteria for Non-target Lesions

Complete Response (CR)	Disappearance of all non-target lesions and normalization of tumor marker level
Incomplete Response/Stable Disease (SD)	Persistence of one or more non-target lesions and or maintenance of tumor marker above normal limits.
Progressive Disease (PD)	Appearance of one or more new lesions and or unequivocal progression of existing non target lesions

Subjects with global deterioration in health status requiring discontinuation of treatment without objective evidence of disease progression will be classified as having symptomatic deterioration. Every effort will be made to document objective progression.

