### **Overall Response Rate**

The best overall response is the best response recorded from the start of treatment until disease progression or recurrence. The objective response rate (ORR) is the proportion of subjects with either a confirmed CR or a confirmed PR as determined using modified RECIST (Version 1.1) criteria, as evaluated by the Investigator. A confirmed CR or PR requires repeat assessments no less than 28 days after the response criteria are first met. Subjects who have not met this criteria for response will be considered non-responders. As the clinical relevance of stable disease (SD) may be important in HCC, subjects with the response of SD will be recorded and documented. Disease control rate defined as CR + PR +SD will be calculated for all subjects treated with PD-0332991.

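### Measurable disease is not an entry criterion, so a patient without a target lesion cannot have a partial response or progress by the 20% rule

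*Combined protocol and SAP*

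**What the plan says.** Section 4.1 defines the disease at entry by diagnosis and refractoriness; its documentation criterion is "Documented HCC by pathologic criteria". None of the 12 inclusion criteria in 4.1 or the 16 exclusion criteria in 4.2 mentions a measurable lesion.

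Section 6.1 separates two kinds of disease. Lesions below the size limits, bone lesions, ascites, effusions, cystic lesions and several others "are considered non-measurable disease". Target lesions are drawn from "All measurable lesions up to a maximum of five lesions per organ and ten lesions in total", and "Non-target lesions include measurable lesions that exceed the maximum numbers per organ or total of all involved organs as well as non-measurable lesions". Non-target lesions need no measurement; only their presence or absence is noted.

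Section 6.2 defines PR for target lesions only: "At least 30% decrease in the sum of the LD of target lesions, taking as reference the baseline sum LD". Non-target disease can be classed as CR, incomplete response/stable disease, or progression, with no PR category.

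Section 7.2 counts a confirmed CR or PR as a response and adds: "Subjects who have not met this criteria for response will be considered non-responders". Section 11.1 analyses tumor response in all subjects. It also describes an analysis population by two cycles of drug and the week 8 assessment. Neither statement refers to measurable disease.

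**The concern.** The response and progression rules presuppose a target-lesion sum that eligibility does not guarantee. Section 5.6 makes the same assumption when it illustrates mild progression by a percentage increase in that sum.

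Two endpoints are touched:

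- **Objective response rate (ORR).** A patient without target lesions stays in the denominator but cannot contribute a PR, which pulls the rate down.
- **TTP (primary).** For that patient no numeric threshold applies. Progression is called by the investigator, who reads the scans in an open-label single-arm study (section 3.0), and the result is compared with a historical median (section 11.0). With no control arm, variation in how progression is called passes straight into the result. The sample is 19 evaluable patients and the futility look comes after 10 events (section 7.1), so one event is 1/10 = 10% of the events at that look.

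**Working it through.** **The plan's own figure.** Section 11.0 gives 19 evaluable patients for alpha 0.05, power 90% and a median TTP of 24 against 12 weeks. If TTP is exponential the hazard ratio is 12/24 = 0.5, and a one-sample test needs (z_alpha + z_beta)² / (ln 2)² events.

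- One-sided 0.05: 17.8, so 18 events; 19 events give 91.6% power.
- Two-sided 0.05: 21.9, so 22 events; 19 events give 85.6% power on the same approximation.

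The 19 is consistent with a one-sided test in which nearly every patient has an event; the plan does not state the sidedness. An entry criterion on measurable disease does not enter this formula, so 19 stands.

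**What a patient without a measurable lesion can and cannot have.**

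| Outcome | Rule | Available without a target lesion? |
|---|---|---|
| PR | 30% fall in target-lesion sum (6.2) | No |
| CR | All non-target lesions gone and tumor marker normal (6.2) | Yes |
| Progression, numeric | 20% rise in target-lesion sum (6.2) | No |
| Progression, new lesion | 6.2 | Yes |
| Progression, unequivocal non-target | 6.2 | Yes |
| Clinical progression | 7.1 | Yes |
| Date of last dose or death if not assessable | 7.1 | Yes |

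**Size.** The documents give no share of patients without measurable disease, so k of 19 is an assumption, shown from 1 to 5. The share of the sample is k/19 and the highest attainable PR rate is (19 − k)/19. If the true PR rate among measurable patients is p, and none of the k has a non-target CR, the observed rate is p(19 − k)/19. The column below takes p = 20%, also an assumption.

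| k | Share of 19 | Highest PR rate | Observed rate if p = 20% |
|---|---|---|---|
| 1 | 5.3% | 94.7% | 18.9% |
| 2 | 10.5% | 89.5% | 17.9% |
| 3 | 15.8% | 84.2% | 16.8% |
| 4 | 21.1% | 78.9% | 15.8% |
| 5 | 26.3% | 73.7% | 14.7% |

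The downward shift is p × k/19. With the 2% sorafenib response rate quoted in section 1.1 used as p, two to four such patients shift ORR by 2% × 2/19 = 0.2 to 2% × 4/19 = 0.4 percentage points. At p = 20% the same range gives 2.1 to 4.2 points. Both are below the 5.3-point step made by one responder.

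**The case against.** The primary endpoint is TTP, which can be assessed without target lesions, and section 6 provides categories for non-target disease. Section 7.2 says how patients who do not meet the response criteria are handled, and counting them as non-responders is conservative. Section 8.1 describes the drug as cytostatic, and ORR is secondary. The population has inoperable, refractory advanced disease, imaged at baseline by CT of chest, abdomen and pelvis and MRI of the liver, with a 10 mm limit on spiral CT. Nothing in the documents shows that anyone will lack a measurable lesion.

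Most of this stands, and it limits the size of the point. It does not answer the gap itself: eligibility does not ensure that the PR rule and the 20% rule can be applied to every patient.

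A reader might infer three stronger things that the documents do not support:

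- *Such patients can never respond.* They cannot have a PR, but a confirmed non-target CR counts in ORR.
- *Their TTP rests only on a judgement of unequivocal progression.* New lesions, clinical progression and the last-dose or death fallback also define the event.
- *The missing criterion causes the subjectivity in TTP.* Clinical progression and non-target progression apply to every patient, and the investigator reads all scans.

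**Conclusion.** The point holds as a minor gap between eligibility and endpoint definitions. A patient with only non-measurable disease may enrol, cannot have a PR, can respond only through a non-target CR, and otherwise counts as a non-responder among all subjects. For TTP that patient loses the only numeric criterion, and what remains is assessed by the unblinded investigator.

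Each such patient is 5.3% of 19. How many there will be is not in the documents; that the number is small in advanced HCC is a judgement. The ORR effect is modest: under the assumptions shown, up to four such patients shift it by less than one responder would. The effect on TTP cannot be quantified from the documents. The sample size is unaffected.

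**What to change.** Add one inclusion criterion to section 4.1: *At least one measurable lesion as defined in section 6.1.* It is checked on the baseline CT and MRI that section 5.1 already requires, so it adds no procedure. The cost is that a few candidates may be excluded.

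For any patient already enrolled without a measurable lesion, keep the all-subjects ORR as the main analysis, add ORR among patients with measurable disease at baseline as a supplementary figure, and list the others separately. Do not replace the main denominator. That would depart from section 11.1, drop patients who could have a non-target CR, and raise ORR through a change made after treatment had begun.

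The criterion makes PR and numeric progression assessable in every new patient. It does not remove subjective progression calls, which remain possible for all patients.

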#### **4.2 Exclusion Criteria**

1. Any concurrent active malignancy requiring treatment (other than basal or squamous cell carcinoma of the skin, carcinoma in situ of the cervix, superficial bladder tumors, or other malignancies curatively treated > 3 years prior to study entry)
2. History of severe cardiovascular disease within the last 12 months: symptomatic congestive heart failure, myocardial infarction, coronary artery disease (CAD), life threatening arrhythmias, uncontrolled hypertension
3. Renal failure requiring hemo- or peritoneal dialysis
4. Unstable systemic diseases or active uncontrolled infection
5. Known history of HIV infection
6. Clinically significant gastrointestinal bleeding within 30 days prior to study entry
7. Major surgery, open biopsy or significant traumatic injury within 4 weeks prior to study entry
8. Child's-Pugh Class C
9. Any malabsorption problem that, in the investigator's opinion, would prevent adequate absorption of the study drug
10. Presence of any other medical complications that in the investigator's opinion, suggests a survival of < 3 months
11. Substance abuse, or medical, psychological or social conditions that may interfere with the patient's participation in the study or evaluation of the study results
12. Patient inability to swallow oral medications
13. Any condition that is unstable or which could jeopardize the safety of the patient and his/her compliance in the study
14. Pregnant or breast-feeding patients
15. Being of reproductive potential and unable or unwilling to practice an effective contraceptive method

16. Lack of positive staining for RB-function on tumor biopsy.

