## **5.1 Visit 1 – Pre-study Evaluation**

Prior to performing study related procedures, subjects will read, understand and sign informed consent. Investigator and medical staff involved will discuss PD-0332991 treatment with potential candidate for the study and obtain informed consent. Pre-study evaluations (other than biopsy) are to be obtained within 28 days prior to start of treatment. These will include:

1. MUGA scan or Echocardiogram if clinically indicated
2. Pulmonary Function Test if clinically indicated
3. CT scan of chest, abdomen, and pelvis
4. MRI of the liver
5. Biopsy if required to confirm diagnosis of HCC and assess RB-pathway status via immunohistochemistry (IHC). PD-0332991 is a highly selective inhibitor of CDK4/6 that is dependent on a functional RB-pathway to exert its anti-proliferative effects. It is inactive against RB-negative tumors. The complete RB-pathway consists of several families of proteins: CDKN(INK4A), D-type cyclins, cyclin-dependent protein kinases (CDK4, CDK6), RB-family proteins, and E2F transcription factors. In addition to RB protein status, overexpression of CDKN (p16INK4A) protein is associated with lack of sensitivity to PD-0332991. In vitro efficacy tests have suggested that Ki67 may be used as a biomarker of cell proliferation and indirectly correlate with sensitivity to PD-0332991. For the current study, IHC of liver biopsy tissue will be used to assess protein expression of RB, p16INK4A and Ki67, which will then be used to determine whether a patient is eligible for trial participation (i.e. likely to show sensitivity to PD-0332991).

The following pre-study evaluations are to be obtained within 14 days prior to start of treatment:

1. Complete history, physical exam including height and weight
2. Performance status, Child-Pugh status

3. Blood cell counts (CBC with differential, platelets) and comprehensive metabolic panel (albumin, alkaline phosphatase, total protein, BUN, creatinine, AST (SGOT), ALT (SGPT), total bilirubin, calcium, sodium, potassium, chloride, bicarbonate), lactate dehydrogenase (LDH), pregnancy test, and TSH, PT/PTT, INR
4. Concomitant medication review

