### **12.3 Protocol Deviations/Exceptions**

Deviations/exceptions from listed eligibility criteria will not be allowed under any circumstances. An accidental or unintentional deviation from the approved protocol, that in the opinion of the investigator, places one or more subjects at increased risk, or affects the rights or welfare of subjects, must be reported to the IRB and DSMC immediately.

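### The albumin entry limit in section 4.1 is printed in mg/dL, so the protocol's only albumin floor excludes essentially nobody; the unit needs confirming and correcting

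*Combined protocol and SAP*

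**What the plan says.** Section 4.1, criterion 10, opens with "Adequate bone marrow, liver and renal function as assessed by the following" and then lists laboratory limits. The albumin item reads "Albumin $\geq 2.5$ mg/dL". The only other limit in that list given as a mass per volume is hemoglobin, "Hemoglobin $\geq 8" g/dL. The remaining liver items are stated as multiples of the upper limit of normal: "Total bilirubin $\leq 1.5" times ULN, and ALT and AST at no more than 5 times ULN.

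Liver function is also restricted elsewhere. Criterion 5 in section 4.1 reads "Be Child's-Pugh class A or B", and exclusion 8 in section 4.2 is "Child's-Pugh Class C". Section 5.1 asks for "Performance status, Child-Pugh status" within 14 days before treatment starts, and the metabolic panel taken in the same window includes albumin.

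Section 12.3 states: "Deviations/exceptions from listed eligibility criteria will not be allowed under any circumstances". Section 15.0 says that audits verify that patients met the eligibility criteria.

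**The concern.** An entry limit is useful only if some candidate could fail it. Albumin is one of three laboratory items in criterion 10 that bear on the liver, alongside bilirubin and ALT/AST. In mg/dL the figure is so small that the item is always met.

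The error cannot be settled from elsewhere in the protocol. Section 8.4 restates entry limits, but only those for hemoglobin, white cells, neutrophils and platelets. Sections 5.1 and 5.3 list albumin as a test without attaching a limit.

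Two things are at stake. First, the authors wrote an albumin limit in addition to the Child-Pugh rule and the other laboratory caps, and as printed it does no work. Second, the no-exceptions rule in section 12.3 makes the printed text the standard for enrolment and audit. Staff must either apply a limit that excludes nobody or silently substitute another, and an auditor cannot check the substitute against the protocol.

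**Working it through.** **Inputs from the documents.** Albumin limit: 2.5 mg/dL (section 4.1, criterion 10). Hemoglobin limit: 8 g/dL (same list). Other liver limits: Child-Pugh A or B, bilirubin at most 1.5 times ULN, ALT and AST at most 5 times ULN (section 4.1); Child-Pugh C excluded (section 4.2). The plan gives no derivation of the albumin limit, so there is no calculation of its own to reproduce.

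**Step 1: convert the unit.** 1 g = 1000 mg, so 2.5 mg/dL ÷ 1000 = 0.0025 g/dL.

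**Step 2: compare with values seen in adults.** Assumption: serum albumin of about 1 to 5 g/dL, from severely low to normal.

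- Lower end: 1 ÷ 0.0025 = 400.
- Upper end: 5 ÷ 0.0025 = 2000.

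The result does not depend on the exact range. If the lower end were ten times too high, at 0.1 g/dL, the limit would still lie 0.1 ÷ 0.0025 = 40 times below it.

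**Step 3: see what the unit used for hemoglobin would give.** 2.5 g/dL × 1000 = 2500 mg/dL, which is 1000 times the printed limit and inside the assumed range. This points to a unit slip. It is an inference from the list, not something the protocol states.

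**Step 4: ask whether another criterion supplies the missing floor.** Bilirubin and ALT/AST are separate measurements. Child-Pugh class does use albumin, but only as one scored item. Assuming the usual scoring, which the protocol does not print (five items of 1 to 3 points, class B at 7 to 9), very low albumin adds no more than 3 points:

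- all other items minimal: 3 + 1 + 1 + 1 + 1 = 7, class B;
- ascites item at its maximum: 3 + 1 + 1 + 1 + 3 = 9, still class B.

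On that scoring, a patient at the maximum albumin score cannot be in class A but can be in class B, however low the albumin is. Child-Pugh class is therefore not an albumin floor.

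**Step 5: trace the effect on the design.** The calculation in section 11.0 (alpha 0.05, power 90%, 19 evaluable patients) uses median times to progression of 12 and 24 weeks. Albumin does not enter it, so none of these figures changes.

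**The case against.** The strongest reply is that this is a slip that misleads nobody. Patients come from one institution's oncology and liver clinics (section 4.0), whose staff would very probably read the limit in g/dL without noticing the printed unit. No wrongly admitted patient can be counted from the documents. This carries weight and keeps the severity low. It does not remove the point, because a criterion that binds without exception should not depend on readers correcting it in their heads.

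A reader might infer several stronger things, which the documents do not support.

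- *That patients with severely reduced liver function can enrol.* Child-Pugh C is barred by both criterion 5 and exclusion 8, and the bilirubin and ALT/AST caps do not depend on the albumin unit. The Child-Pugh arithmetic shows only that the class is not an albumin floor; it leads to class B, which the protocol deliberately admits.
- *That a site would have no ground to refuse a patient with very low albumin.* Section 4.2 excludes unstable systemic disease (exclusion 4), complications suggesting survival under 3 months (exclusion 10), and conditions that could endanger the patient (exclusion 13). Criterion 4 requires a life expectancy above 3 months. Section 12.3 makes these equally binding.
- *That such patients face higher drug exposure.* Section 10.3 reports pre-clinical evidence of CYP3A4 metabolism, but nothing in the protocol links albumin to clearance or toxicity.
- *That the primary endpoint is disturbed.* Section 11.1 restricts the efficacy set to patients with two cycles and a week 8 assessment and replaces those who are not evaluable. Section 7.1 uses the date of last dose or death when disease could not be assessed. No bias attributable to the albumin limit can be derived from these rules or sized.

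**Conclusion.** The criterion is wrong as written, and the severity is minor. Its printed value is 0.0025 g/dL, about 400 to 2000 times below measured values if adult albumin runs from about 1 to 5 g/dL. The protocol's only albumin floor therefore excludes essentially nobody.

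The practical consequence is narrow. A patient in an admitted Child-Pugh class who meets all the other limits, and whom the investigator does not exclude on judgement, could enter with very low albumin. The item also cannot be audited in any meaningful way.

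The conclusion rests on the assumed albumin range, to which it is insensitive. That g/dL was intended is likely but unproven.

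**What to change.** The sponsor should confirm the intended unit and value of the albumin limit and correct criterion 10 in section 4.1 accordingly. Hemoglobin in the same list is given in g/dL, which is a reason to ask about the unit first; this review does not choose the limit. The confirmed limit should be carried into any eligibility worksheet in use, and any patients already enrolled should be checked against it.

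The cost is a one-word amendment if only the unit is wrong. No new test is needed, because section 5.1 already includes albumin at screening. A few candidates may become ineligible. The sample size, alpha, power and planned analysis stay as they are.
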